13.1.3 Sight Threatening Adverse Events

Of the postoperative adverse events listed in Section 13.1.2, the following are pre-defined as sight threatening and must therefore be reported as Serious Adverse Events (SAEs) per the guidelines for reporting in Section 13.3:

- ≠ Persistent (at time of study exit) BCDVA loss of 3 or more lines compared to best BCDVA achieved during the course of study
- ≠ Endophthalmitis
- ≠ Corneal decompensation
- ≠ Retinal detachment
- ≠ Severe choroidal hemorrhage or detachment
- ≠ Aqueous misdirection

Other adverse events may also be considered potentially sight threatening, or may meet other seriousness criteria. Any adverse event meeting any SAE seriousness criterion, as defined in the Glossary of Terms, must be reported as an SAE per Section 13.3.

13.1.4 Other Postoperative Events/Findings

The following events are anticipated postoperative events. In the absence of an untoward effect to the subject, these should not be reported as AEs. These findings will be captured on the eCRF under Gonioscopy, Slit Lamp Examination, or IOP findings, etc.

- a) AC shallowing
- b) Chemosis
- c) CyPass intraluminal blood
- d) Early hypotony
- e) Focal peripheral anterior synechiae
- f) Microhyphema
- g) Partial obstruction of CyPass lumen
- h) Pigment dispersion

- i) Posterior synechiae
- j) Pseudophacodenesis
- k) Pupillary miosis
- l) Schlemm's intracanalicular blood
- m) Transient forward IOL movement related to AC shallowing

13.1.5 **Device Deficiencies**

A device deficiency may or may not be associated with subject harm (ie, ADE or SADE); however, not all ADEs or SADEs are due to a device deficiency. The Investigator should determine the applicable category for the identified or suspect device deficiency and report any patient harm separately. Examples of device deficiencies include, but are not limited to the following:

- ≠ Failure to meet product specifications
- ≠ CyPass applicator issues
 - Guidewire bent
 - Inability to retract the guidewire
 - Deployment button resistance
 - Inability to deploy CyPass Micro-Stent due to applicator performance or design
- ≠ CyPass Micro-Stent issues
 - CyPass Micro-Stent damage
 - Defective CyPass Micro-Stent surface or interior lumen
- ≠ Other device issues
- ≠ Packaging issue
 - Pouch not sealed

13.2 **Monitoring for Adverse Events**

At each visit, after the subject has had the opportunity to spontaneously mention any problems, the Investigator should inquire about AEs by asking the standard questions:

- ≠ “Have you had any health problems since your last study visit?”
- ≠ “Have there been any changes in the medicines you take since your last study visit?”

13.3 **Procedures for Recording and Reporting**

AEs are collected from the time of informed consent. Any preexisting medical conditions or signs/symptoms present in a subject prior to the start of the study (ie, before informed consent is signed) are not considered AEs in the study and should be recorded in the Medical History section of the eCRF. However, a worsening of the pre-existing medical condition or signs/symptoms are considered AEs.

In addition, aqueous cells and flare, corneal edema, raised IOP and superficial punctate keratitis are examples of early postoperative findings that are typically observed following ocular surgery. These are not considered AEs if they are not severe in nature or can reasonably be expected to resolve within a month and not result in any untoward long term visual outcome impact. The Investigator must assess and determine whether an AE has occurred.

All ocular AEs for the study eye and the contralateral non-study eye, as well as non-ocular AEs, must be reported as part of this study.

For each recorded event, the ADEs and SAEs documentation must include: date of occurrence, severity, treatment (if applicable), outcome, and assessments of the seriousness and causality. In addition, the Investigator must document all device deficiencies reported or observed with test and control articles on the Device Deficiency eCRF. The site must submit all available information on ADEs, SAEs, and device deficiencies to the Study Sponsor immediately as follows:

- ≠ All SAEs must be reported immediately (within 24 hours) of the Investigator's or site's awareness.
- ≠ ADEs that do not meet seriousness criteria and device deficiencies must be reported within 10 calendar days of the Investigator's or site's awareness.

A printed copy of the completed *Serious Adverse Event and Adverse Device Effect* and/or *Device Deficiency* eCRF must be included with product returns.

- ≠ Additional relevant information after initial reporting must be entered into the eCRF as soon as the data become available.
- ≠ Document any changes to concomitant medications on the appropriate eCRFs.
- ≠ Document all relevant information from Discharge Summary, Autopsy Report, Certificate of Death etc., if applicable, in narrative section of the *Serious Adverse Event and Adverse Device Effect* eCRF.

Note: Should the EDC system become non-operational, the site must complete the appropriate paper *Serious Adverse Event and Adverse Device Effect* and/or *Device Deficiency* Form. The completed form is faxed or emailed to the Study Sponsor at [name] according to the timelines outlined above; however, the reported information must be entered into the EDC system once it becomes operational.

Any AEs and device deficiencies for non-study marketed devices/products will be considered and processed as spontaneous (following the post-market vigilance procedures) and should be communicated to the device's/product's manufacturer as per local requirements.

Study Sponsor representatives may be contacted for any protocol related question and their contact information is provided in the Manual of Procedures that accompanies this protocol.

Further, depending upon the nature of the AE or device deficiency being reported, the Study Sponsor may request copies of applicable portions of the subject's medical records. The Investigator must also report all AEs and device deficiencies that could have led to a SADE according to the requirements of regulatory authorities or IRB/IEC.

13.3.1 Intensity and Causality Assessments

Where appropriate, the Investigator must assess the intensity (severity) of the AE based on medical judgment with consideration of any subjective symptom(s), as defined below:

Intensity (Severity)

Mild	An AE is mild if the subject is aware of but can easily tolerate the sign or symptom.
Moderate	An AE is moderate if the sign or symptom results in discomfort significant enough to cause interference with the subject's usual activities.
Severe	An AE is severe if the sign or symptom is incapacitating and results in the subject's inability to work or engage in their usual activities.

For every AE in the study, the Investigator must assess the causality (Related or Not Related to the medical device or study procedure). An assessment of causality will also be performed by Study Sponsor utilizing the same definitions, as shown below:

Causality

Related	An AE classified as related may be either definitely related or possibly related where a direct cause and effect relationship with the medical device or study procedure has not been demonstrated, but there is a reasonable possibility that the AE was caused by the medical device or study procedure.
Not Related	An AE classified as not related may either be definitely unrelated or simply unlikely to be related (ie, there are other more likely causes for the AE).

The Study Sponsor will assess the AEs and may upgrade the Investigator's assessment of seriousness and/or causality. The Study Sponsor will notify the Investigator of any AEs that is upgraded from non-serious to serious or from unrelated to related.

13.4 Return Product Analysis

Study Sponsor representatives and their contact information are provided in the MOP that accompanies this protocol.

Alcon products associated with device deficiencies and/or product related AEs should be returned and must include the Complaint # which will be provided by Study Sponsor after the case is entered in the Study Sponsor's Global Product Complaint Management System (GPCMS).

13.5 Unmasking of the Study Information

Not applicable; this study is open-label.

13.6 Follow-Up of Subjects with Adverse Events

The Investigator is responsible for adequate and safe medical care of subjects during the study and for ensuring that appropriate medical care and relevant follow-up procedures are maintained after the study.

The Investigator should provide the Study Sponsor with any new safety information (which includes new AEs and changes to previously reported AEs) that may affect the safety evaluation of the device. For AEs that are unresolved/ ongoing at time of subject exit from study, any additional information received at follow-up should be documented in the eCRFs up to study completion (ie, database lock).

All complaints received after this time period will be considered and processed as spontaneous (following the post-market vigilance procedures) and should be communicated to the medical device's manufacturer as per local requirements.

The Investigator should also report complaints on non-Alcon products directly to the manufacturer as per the manufacturer's instructions or local regulatory requirements.

13.7 Pregnancy in the Clinical Study

Pregnancy is not reportable as an AE; however, complications may be reportable and will be decided on a case-by-case basis. An Alcon form will be utilized to capture all pregnancy-related information until birth of the child.

14 DATA REVIEW AND HANDLING

14.1 Completion of Source Documents and Case Report Forms

The nature and location of all source documents must be identified to ensure that original data required to complete the eCRFs exist and are accessible for verification by the monitor. If electronic source records are maintained, the EMR system will be reviewed for 21 CFR Part 11 compliance and the method of verification will be determined in advance of starting the study. Data reported on the eCRFs must be derived from source documentation and be consistent with source documentation, and any discrepancies must be explained in writing. At a minimum, source documentation must include the following information for each subject:

- # Subject identification (name, sex)
- # Documentation of subject eligibility
- # Date of informed consent, and a copy of signed informed consent form
- # Dates of visits
- # Documentation that protocol-specific procedures were performed
- # Results of study assessments, as required by the protocol
- # Documentation of AEs and other safety parameters (as applicable)
- # Records regarding medical histories and the use of concomitant therapies prior to and during the study
- # Date of study completion and reason for early discontinuation (if applicable)

It is required that the author of each entry in the source documents be identifiable (eg, initials or signature and date). Any change or correction to data reported in the source, or on a eCRF, must be dated, initialed, and explained if necessary. Changes must not obscure the original entry (ie, an audit trail must be maintained). Direct access to source documentation (medical records) must be allowed for the purpose of verifying that the data recorded on the eCRF are consistent with the original source data.

EDC is designated for data collection and should be completed by designated individuals only. Required examinations must be recorded on the eCRFs. All data reported must have corresponding entries in the source documents. The Investigator will review the reported data and certify that the eCRFs are accurate and complete as indicated by signature. Subject identifiers must not be recorded on the eCRFs beyond subject number, demographics information, and/or other study identifiers.

Deviations from this protocol, regulatory requirements, and Good Clinical Practice (GCP) must be recorded in the study records. An explanation of the deviation should be included, as applicable. In addition, corrective and preventive action should be identified, implemented, and documented within the study records.

14.2 Data Review and Clarifications

Upon completion of the eCRFs, the data will be reviewed by Alcon study personnel for accuracy and completeness. If corrections and/or any additions to the data are deemed necessary, queries will be generated by Alcon data management or the site management (study monitor) team and forwarded to the investigative site. Staff at each site are expected to respond to data queries in a timely manner and ensure that the corrections and changes made to the data in the EDC system are reflected in the subjects' source documentation. In addition, prior to study start (first subject first visit) a plan for data validation will be completed by Alcon Clinical Data Management and agreed upon by members of the Clinical Trial Management (CTM) team.

Concomitant medications entered into the database will be coded using the current version of the WHO (World Health Organization) Drug Reference List. Medical history and adverse events will be coded using the medical dictionary for regulatory activities (MedDRA) terminology.

Upon completion of the study and once the database is declared complete and accurate, the database will be locked and data will be available for the final data analysis. Any changes to the database after lock will be implemented upon agreement between Alcon's clinical trial management and biostatistics department, and will be completed following Alcon's procedures for changes to a database after database lock.

15 ANALYSIS PLAN

This information may also be contained within a separate biostatistical analysis plan which will be prepared and finalized prior to database lock.

15.1 Subject Evaluability

All patients will be considered enrolled once they have signed the informed consent form. The assignment of each study eye to the study analysis sets will be made prior to database lock.

15.2 Analysis Data Sets

All eligible subjects will be screened to determine if they meet all inclusion and no exclusion criteria. Subjects who do so and provide informed consent will be considered enrolled in the study.

15.2.1 Intention to Treat

The intention to treat (ITT) analysis set will be defined as the set of study eyes for which a CyPass Micro-Stent implant is attempted; the ITT analysis set will be the primary analysis set for all study analyses.

15.3 Demographics and Baseline Characteristics

Demographics and baseline characteristics will be summarized with appropriate summary statistics. Eye level summaries will be based on all study eyes in the ITT analysis set; subject level summaries (eg, age) will be based on all subjects with an eye in the ITT analysis set.

15.4 Effectiveness Analyses

15.4.1 Primary Effectiveness

There is no primary effectiveness endpoint for this study.

15.4.2 Secondary Effectiveness

The secondary effectiveness endpoints are listed in Section 8.2.1.2.

15.4.2.1 Statistical Hypotheses

There are no statistical hypotheses for the secondary effectiveness endpoints which will be summarized descriptively.

15.4.2.2 Analysis Methods

Continuous endpoints will be summarized by number of observations (n), mean, median, standard deviation, minimum and maximum; binary endpoints will be summarized by numerator (number of eyes meeting the endpoint), denominator, and the proportion of ITT eyes meeting the endpoint. Denominators for adverse events, slit lamp findings, and other events will be the number of eyes in the ITT set. Denominators for data such as visual acuity and other subject data that is collected at protocol-required visits will reflect the number of eyes with non-missing data in the ITT set. Summary statistics will be presented at all postoperative visits for which the endpoint data are collected. Supportive analysis will be conducted using the DI analysis set for all secondary effectiveness outcomes.

15.5 Safety Analyses

15.5.1 Primary Safety

The primary safety endpoint is detailed in Section 8.2.2.1.

15.5.1.1 Statistical Hypothesis

The primary null hypothesis to be tested is that the observed rate of clinically relevant complications associated with CyPass Micro-Stent placement and stability is greater than or equal to the performance target rate of 7%. The corresponding alternative hypothesis to be tested is that the observed rate of complications is less than the performance target rate. These hypotheses are expressed formulaically as:

$$H_0: p_C \geq 7\%$$

$$H_1: p_C < 7\%$$

where p_C is the population proportion of eyes experiencing a complication event at 36 months.

15.5.1.2 Analysis Methods

The primary safety hypothesis will be tested with an exact one-sided binomial test with type I error 0.05. The ITT analysis set will be used for the primary safety analysis.

15.5.2 Secondary Safety

The secondary safety endpoints are listed in Section 8.2.2.2.

15.5.2.1 Statistical Hypotheses

There are no statistical hypotheses for the secondary safety endpoints.

15.5.2.2 Analysis Methods

Continuous endpoints will be summarized by number of observations (n), mean, median, standard deviation, minimum and maximum; binary endpoints will be summarized by numerator (number of eyes meeting the endpoint), denominator (number of eyes in the ITT set), and the proportion of eyes meeting the endpoint. Summary statistics will be presented at all follow-up visits for which the endpoint data are collected. Supportive analysis will be conducted using the DI analysis set for all secondary safety outcomes.

15.5.3 Other Safety

The other safety endpoints are listed in Section 8.2.2.3.

15.5.3.1 Statistical Hypotheses

There are no statistical hypotheses for the other safety endpoints.

15.5.3.2 Analysis Methods

Continuous endpoints will be summarized by number of observations (n), mean, median, standard deviation, minimum and maximum; binary endpoints will be summarized by numerator (number of eyes meeting the endpoint), denominator (number of eyes in the ITT set), and the proportion of eyes meeting the endpoint. Summary statistics will be presented at all follow-up visits for which the endpoint data are collected. Supportive analysis will be conducted using the DI analysis set for all other safety outcomes.

15.5.4 Ocular Adverse Events

The number of events, number of eyes experiencing the event, and the rate of the event will be reported for all postoperative ocular adverse events occurring in study eyes. Any ocular events occurring pre-operatively in study eyes will be listed separately. Any ocular events occurring in non-study eyes will also be listed separately.

15.5.5 **Non-Ocular Adverse Events**

The number of events, number of subjects experiencing the event, and the rate of the event will be reported for all non-ocular adverse events.

15.5.6 **Device Deficiencies**

The number of device deficiencies by type will be calculated, and a listing of all device deficiencies will be provided.

15.5.7 **Endothelial Cell Count**

Specular microscopy data at baseline and at each follow-up visit at which the exam is conducted will be summarized with number of observation (n), mean, median, standard deviation, minimum, and maximum. Change and percentage change from baseline as well as change between two consecutive visits will also be summarized with number of observations (n), mean, median, standard deviation, minimum, and maximum.

15.5.8 **Slit Lamp and Fundus Examinations**

Slit lamp and fundus examination results at baseline and at each follow-up visit at which the exams are conducted will be summarized by the number of subjects in each category (numerator), the number of subjects with data (denominator), and the percentage of subjects in each category (numerator / denominator).

15.5.9 **Corneal Pachymetry**

Corneal pachymetry data recorded at screening and at each follow-up visit at which the exam is conducted will be summarized descriptively with number of observations (n), mean, median, standard deviation, minimum, and maximum.

15.5.10 **Visual Field Loss Mean Deviation Testing**

The visual field mean deviation testing data collected at baseline and at each follow-up visit at which the exam is conducted will be summarized with number of observations (n), mean, standard deviation, minimum, and maximum.

15.5.11 **Manifest Refraction**

The number of observations (n), mean, median, standard deviation, minimum, and maximum for sphere, cylinder, and manifest refraction spherical equivalent will be reported at baseline and at each follow-up visit for which manifest refraction is scheduled.

15.6 Handling of Missing Data

A tipping point analysis will be performed for the primary safety endpoint.

In addition, a comparison of baseline characteristics including age, gender, race, site, and baseline unmedicated IOP will be performed between those subjects who complete Visit 8 (36 Month Follow-up) and those who do not.

15.7 Interim Analyses

Interim reports pertaining to the progress of the post approval study will be submitted to the FDA for review every 6 months for the first two years, starting from the date of approval, and will continue to be submitted annually thereafter, until study completion.

For each interim report, the number of subjects enrolled and implanted with the CyPass device will be reported. In addition, the number of clinically relevant complications associated with CyPass Micro-Stent placement and stability (events toward the primary endpoint) will be reported, and a listing and summary table with the number of events, and number and proportion of subjects experiencing all such events will be provided. A listing of all ocular SAEs will also be provided. A summary of the secondary effectiveness endpoints will be reported once 50% of the subjects in the ITT set have completed Visit 5 (6 Month Follow-up Visit).

15.8 Sample Size Justification

The performance target for the primary safety endpoint is 7.0%.

An evaluation of COMPASS (TMI-09-01) data showed that through 24 months of follow-up, there were two eyes with failures to implant and eight eyes with CyPass malposition events, respectively, corresponding to the above definitions. In addition, there were four eyes with documentation of three rings visible within the first postoperative week that likely would have undergone early secondary surgical intervention due to anterior CyPass positioning under the approach documented in the Instructions for Use (IFU). Inclusion of these cases would increase the number of observed events from 10 to 14 (3.74%, 95% confidence interval: 2.1% – 6.2%). Of note, not all investigators documented the number of rings visible in the early postoperative period because this was not a study requirement (data regarding the number of rings is recorded for only 96 subjects at 1 Day and 139 subjects at 1 Week), so this number likely underestimates the number of subjects who would have been candidates for early surgical re-intervention under the new criteria described in the IFU.

Based on these considerations, the “true” event rate is assumed to be 4.0%, and the performance target is set to 7.0%. The following assumptions were used for the sample size calculation:

- ≠ Type I error = 0.05
- ≠ one-sided alternative

With a sample size of 360 subjects in the final analysis (unilateral implants only) and a performance target of 7.0%, assuming a true event rate of 4.0%, there is 80% power to reject the null hypothesis based on a one-sided alpha = 0.05-level exact test for a single proportion.

To allow for attrition over this 36-month study, a cumulative rate of up to 20% of subjects lost to follow-up is assumed, corresponding to a targeted implantation of 450 eyes in 450 subjects to achieve at least 360 eyes with 36 months of follow-up.

Annex F of ANSI standard Z80.27-2014 refers to ensuring adequate sample size so that any adverse event of a given type that occurs in the population at a rate of 1% or greater is likely to be seen in the study. With 360 subjects, there is at least 97% probability that at least one adverse event will be detected, assuming a true rate of 1.0%. There is at least 95% probability if the true rate is 0.83%.

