6.2.2 Analysis Methods

The primary safety hypothesis will be tested with an exact one-sided binomial test with type I error 0.05. This endpoint will be summarized by numerator (number of eyes meeting the endpoint), denominator (number of eyes in the ITT set), and the rate of ITT eyes meeting the endpoint. In addition, a summary of each individual complication type included in the primary safety endpoint (and a listing of these complications) will be provided.

Otherwise, no formal statistical hypothesis testing is planned for this study.

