6.5.11 CyPass Explantation and/or Repositioning

A listing detailing subjects with CyPass explantation and/or repositioning will be provided. The listing will include the following variables: site-subject, age, sex, race, ethnicity, explantation or repositioning event, surgery date, study day, and reason. The data for this listing will be collected on the adverse events eCRF. Further details can be found in Appendix C: Data Sources.

7 Sample Size and Power Calculations

The performance target for the primary safety endpoint is 7.0%.

An evaluation of COMPASS (TMI-09-01) data showed that through 24 months of follow-up, there were two eyes with failures to implant and eight eyes with CyPass malposition events, respectively, corresponding to the above definitions. In addition, there were four eyes with documentation of three rings visible within the first postoperative week that likely would have undergone early secondary surgical intervention due to anterior CyPass positioning under the approach documented in the Instructions for Use (IFU). Inclusion of these cases would increase the number of observed events from 10 to 14 (3.74%, 95% confidence

interval: 2.1% – 6.2%). Of note, not all investigators documented the number of rings visible in the early postoperative period because this was not a study requirement (data regarding the number of rings is recorded for only 96 subjects at 1 Day and 139 subjects at 1 Week), so this number likely underestimates the number of subjects who would have been candidates for early surgical re-intervention under the new criteria described in the IFU.

Based on these considerations, the “true” event rate is assumed to be 4.0%, and the performance target is set to 7.0%. The following assumptions were used for the sample size calculation:

- ≠ Type I error = 0.05
- ≠ one-sided alternative

With a sample size of 360 subjects in the final analysis (unilateral implants only) and a performance target of 7.0%, assuming a true event rate of 4.0%, there is 80% power to reject the null hypothesis based on a one-sided alpha = 0.05-level exact test for a single proportion.

To allow for attrition over this 36-month study, a cumulative rate of up to 20% of subjects lost to follow-up is assumed, corresponding to a targeted implantation of 450 eyes in 450 subjects to achieve at least 360 eyes with 36 months of follow-up.

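### The 80% power is computed for 360 eyes, but the primary test is specified on the ITT set of about 450; the two sample sizes are not reconciled

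*Protocol*

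**What the plan says.** **Sizing.** Protocol 15.8, repeated in the synopsis and SAP 7, sets a performance target of 7.0%, an assumed true rate of 4.0%, "Type I error = 0.05" and a "one-sided alternative". SAP 7 attaches 80% power to one sample size: "With a sample size of 360 subjects in the final analysis (unilateral implants only"). The next paragraph allows for up to 20% loss to follow-up and targets 450 implanted eyes "to achieve at least 360 eyes with 36 months of follow-up". Protocol 7.2 also describes the 360 as the evaluable subjects with 36-month data.

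**Analysis.** Protocol 15.5.1.2 says: "The primary safety hypothesis will be tested with an exact one-sided binomial test with type I error 0.05". It adds: "The ITT analysis set will be used for the primary safety analysis". Protocol 15.2.1 and SAP 2.1 define ITT as all study eyes in which an implant is attempted. The rate formula in SAP 6.2 divides by the number of subjects in the ITT set, and SAP 6.2.2 repeats it: "denominator (number of eyes in the ITT set), and the rate of ITT eyes meeting the endpoint".

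**Incomplete eyes.** SAP 3 allows no imputation and gives a general convention of non-missing denominators for percentages. Protocol 15.6 plans a tipping point analysis for the primary endpoint; the SAP does not describe one. Protocol 12.4 says that subjects with an implant or a failed implantation are not replaced if they discontinue.

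**The concern.** The sizing text treats the final analysis as 360 eyes with 36-month data. The analysis text uses every ITT eye as the denominator, and loss to follow-up does not remove an eye from that set. With about 450 eyes attempted, the planned test has about 450 eyes, not 360.

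This is the study's only formal hypothesis test, and neither document states the largest number of events compatible with success. A reader working from the sizing text would derive 17; a reader working from the analysis text would derive 22.

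The choice also affects the error rate. With all ITT eyes in the denominator and no imputation, an eye lost before 36 months counts as event-free unless its event was recorded before it left.

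**Working it through.** **Inputs.** Null rate 7.0%, true rate 4.0%, one-sided level 0.05 and n = 360 (Protocol 15.8); exact binomial test on ITT (Protocol 15.5.1.2); 450 implanted eyes and up to 20% attrition (Protocol 15.8).

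**Method.** For each n, find the largest c with P(X ≤ c | n, 0.07) ≤ 0.05. Power is then P(X ≤ c | n, 0.04).

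**1. The plan's own figure, n = 360.**
- P(X ≤ 17 | 360, 0.07) = 0.0499 and P(X ≤ 18 | 360, 0.07) = 0.0783, so c = 17.
- Power = P(X ≤ 17 | 360, 0.04) = 0.8016. The stated 80% is reproduced.
- Attrition: 360 / (1 − 0.20) = 450. Also reproduced.

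**2. The test as specified, n = 450.**
- P(X ≤ 22 | 450, 0.07) = 0.0429 and P(X ≤ 23 | 450, 0.07) = 0.0649, so c = 22.
- Nominal power = P(X ≤ 22 | 450, 0.04) = 0.8597.
- The ITT count will not be exactly 450, since failed implantations belong to it. The result changes little: 86.4% at 448 and 84.8% at 455, both with c = 22.

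| Denominator | Maximum events | Attained level | Power at 4.0% |
|---|---|---|---|
| 360 eyes with 36-month data | 17 | 0.0499 | 80.2% |
| 450 ITT eyes | 22 | 0.0429 | 86.0% |

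**3. What the ITT figures assume about lost eyes.** Illustrative assumptions, not in the documents: 90 of 450 eyes are lost (20%), the true 36-month rate is 7% in all eyes, and a fraction f of the lost eyes' events is recorded before loss. The count is then Bin(360, 0.07) + Bin(90, 0.07f), and the test rejects at 22 or fewer.

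| f | Expected recorded rate, (360 × 0.07 + 90 × 0.07f) / 450 | Type I error |
|---|---|---|
| 1 | 7.00% | 4.3% |
| 0.75 | 6.65% | 7.5% |
| 0.5 | 6.30% | 12.6% |
| 0 | 5.60% | 29.6% |

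**4. If the denominator is eyes with 36-month data.** The number would then vary around the design value, and exact-test power is not monotone in n:

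| n | Maximum events | Power at 4.0% |
|---|---|---|
| 350 | 16 | 75.9% |
| 359 | 16 | 72.7% |
| 360 | 17 | 80.2% |
| 370 | 17 | 76.9% |
| 376 | 17 | 74.9% |
| 377 | 18 | 81.8% |
| 380 | 18 | 80.9% |

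From 350 to 380 eyes, power runs from about 73% (at 359) to 82% (at 377).

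**The case against.** The strongest reply is that nothing is miscalculated. The 80% is right at 360, and sizing at one number and inflating for attrition is standard practice. If ITT is tested, nominal power is higher than stated, so sizing on 360 is conservative. All of this stands as arithmetic. It does not remove the mismatch, and the conservative reading holds only if the lost eyes' events are captured, which the plan does not say.

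Three stronger readings are tempting, and the documents do not support them.

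- *That the plan promises 80% for any number from 360 upward.* It does not. The power sentence names 360 only. The words "to achieve at least 360 eyes with 36 months of follow-up" come in the following paragraph as a retention goal. Variation around a design number is a property of every exact test.
- *That the 80% corresponds to no analysis at all.* This goes too far. Protocol 7.2 calls the 360 evaluable, and SAP 3 has a general non-missing convention, so a 36-month-data denominator may have been intended. But the text specific to the primary endpoint says ITT, and no separate completer test is planned.
- *That expected power is really below 80%.* This needs both the 36-month-data denominator and an attrition model. If completers follow Bin(450, 1 − attrition), mean power is 76.6% at 20% attrition, 79.1% at 15% and 81.2% at 10%. Protocol 15.8 says up to 20% and Protocol 7.2 says approximately 20%, so no one of these figures can be given as the study's power.

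**Conclusion.** The point holds as an unreconciled sample size, not as an arithmetic error. The sizing sections describe a test on 360 eyes (17 events, 80.2%); the endpoint and analysis sections specify one on about 450 ITT eyes (22 events, 86.0% nominal). The stated sample size and power do not describe the primary test as written.

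On the plan's own rates the study is not underpowered under ITT. The 86.0% and the 5% level assume that events in eyes lost before 36 months are recorded. The type I error figures above show how sensitive the level is to that assumption; they rest on 90 lost eyes and a 7% true rate and are not a forecast. The tipping point analysis in Protocol 15.6 bears on this as a sensitivity analysis but does not settle the primary denominator. As a matter of sample-size wording this is minor; the handling of lost eyes is the part with consequences.

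**What to change.** In the synopsis, Protocol 15.8 and SAP 7, name the denominator of the primary test and give the event limit and power that belong to it:

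- **If ITT is kept:** for 450 eyes, at most 22 events, nominal power 86.0%. State that this power and the 5% level assume that events in eyes lost before 36 months are captured, and say how eyes without 36-month data are counted.
- **If eyes with 36-month data are meant:** for 360 eyes, at most 17 events, power 80.2%. Note that power varies from about 73% to 82% for 350 to 380 eyes, and bring Protocol 15.5.1.2 and SAP 6.2 and 6.2.2 into line.

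The first option changes sample-size wording only; the second also needs the matching edit to the analysis sections. Neither needs new data, procedures or subjects.
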